### 7.2 Subject Exclusion Criteria

Subjects who meet any of the following criteria will not be eligible to participate in this study.

1. Has clinically significant infection (e.g., pneumonia, pyelonephritis) or chronic infection within 30 days prior to enrollment.
2. Has evidence of unstable or uncontrolled, clinically significant cardiovascular, central nervous system, pulmonary, hepatic, renal, gastrointestinal, genitourinary, hematological, coagulation, immunological, endocrine/metabolic, or other medical disorder, including serious allergy, asthma, hypoxemia, hypertension, seizures, or allergic skin rash, that, in the opinion of the Investigator, would confound the study results or compromise subject safety.

3. Has estimated glomerular filtration rate (eGFR) <30 mL/min/1.73 using the Modification of Diet in Renal Disease [MDRD] formula.
4. Has liver disease or dysfunction characterized by Child-Pugh Class B or Class C.
5. History of any major neurological disorders, including stroke, multiple sclerosis, brain tumor, or neurodegenerative disease.
6. Has active psychiatric problems that, in the Investigator's opinion, may interfere with compliance with the study procedures.
7. Is unable to participate in all the study visits or comply with study procedures.
8. Has history of breast implants, breast augmentation, or breast reduction surgery.
9. Has a prior history of difficulty establishing lactation.
10. Gastrointestinal conditions or procedures (including weight loss surgery; e.g., Lap-Band® or gastric bypass) that may affect drug absorption.
11. Any history of malignancy (with the exception only of basal or squamous cell carcinoma of the skin in individuals that have been cancer free for >5 years).
12. History within the last 2 years of drug, alcohol, amphetamine and derivatives, or cocaine abuse. Subjects with amphetamine derivatives prescribed by and under the care of a health care practitioner can be enrolled after evaluation by the Investigator.
13. Current smoker.
14. Blood donation, participation in a multiple blood draw clinical study, major trauma, or surgery with or without blood loss within 30 days prior to enrollment.
15. Blood transfusion for any reason within 90 days prior to enrollment.
16. Use of any HMG Co-A reductase inhibitor (statin) concurrently or within 30 days prior to enrollment.
17. Use of cyclosporine, cholestyramine, probenecid, fibrate drugs, or medications contraindicated during lactation concomitantly or within 30 days prior to randomization (Visit T1).
18. Concomitant use or use within 30 days prior to randomization (Visit T1) of drugs that decrease breast milk production, such as pseudoephedrine
19. Concomitant use or use within 30 days prior to randomization (Visit T1) of drugs that increase breast milk production, such as domperidone.
20. Use of any experimental or investigational drugs/vaccines concurrently or within 30 days or 5 half-lives of the drug, whichever is longer, prior to screening (Visit S1).
21. Any current condition that in either the Investigator's, Sponsor's, or authorized Medical Monitor's opinion may compromise subject safety or ability to complete the study or interfere with study data interpretation.
22. An employee or contractor of the facility conducting the study, or a family member of the Principal Investigator, Co-Investigator, or Sponsor.

### **7.3 Screen Failures**

Subjects who sign the ICF and enter the screening period of the study but do not meet all eligibility criteria at the time of randomization (Visit T1) will be considered a screen failure and will not be randomized into the study.

## **8. TREATMENT OF SUBJECTS**

### **8.1 Administration of Investigational Medicinal Product**

On Day 1 (Visit T1) of the Treatment Period, subjects will be randomized to receive bempedoic acid (Cohort 1) or bempedoic acid/ezetimibe FCDP (Cohort 2). Each dose of IMP is comprised of 1 tablet from a bottle. The CRU staff will administer IMP to subjects in the unit on Day 1 and Day 6 of the study. The IMP will be self-administered by subjects on Day 2 through Day 5 at home. Subjects will be instructed to take IMP once daily at approximately the same time each morning ( $\pm$  2 hours) with or without food. On the evening of Day 5 (Visit T2), subjects will check-in to the CRU and CRU staff will administer IMP on the morning of Day 6.

Study staff will call subjects on Days 2 through Day 5 to ensure they are taking IMP appropriately. Day and time of IMP administration must be captured in the Study Drug Diary. If the subject forgets to take IMP at the same time ( $\pm$  2 hours) Day 2 through Day 5, it may be taken up to 6 hours later the same day. After that, the subject should not take IMP that day and the Sponsor should be contacted to determine if the subject should continue or be replaced in the study. The details describing the reason for the missed dose should be documented in the subject's medical record. Extra IMP is provided and can be used to replace a dose of IMP that cannot be used if lost or damaged.

Other details regarding IMP including description, supply and control, accountability, handling, and disposal are provided in [Section 0](#).

### **8.2 Prior and Concomitant Medications**

Any medication or vaccine (including over the counter or prescription medicines, vitamins, and/or herbal supplements) that the subject is receiving at the time of enrollment or receives during the study must be recorded in the eCRF along with:

- reason for use,
- dates of administration including start and end dates, and
- dosage information including dose and frequency.

Subjects will be permitted to take concomitant medications except those listed in [Section 8.2.1](#).

#### **8.2.1 Prohibited Medications**

Subjects may not use medications listed below within the time periods indicated and may not use the following drugs during the study:

- HMG Co-A reductase inhibitor (statin) concurrently or within 30 days prior to randomization (Visit T1);
- cyclosporine, cholestyramine, probenecid, fibrate drugs, or medications contraindicated during lactation concurrently or within 30 days prior to randomization (Visit T1);
- experimental or investigational drugs concurrently or within 30 days or 5 half-lives of the drug, whichever is longer, prior to screening (Visit S1);

- concomitant use or use within 30 days prior to randomization (Visit T1) of drugs that decrease breast milk production, such as pseudoephedrine; or
- concomitant use or use within 30 days prior to randomization (Visit T1) of drugs that increase breast milk production, such as domperidone.

### **8.2.2 Permitted Medications**

Concomitant use of prescription or nonprescription medications, vaccines and supplements not listed in [Section 8.2.1](#) are allowed during the study, upon prior consent of the Investigator (or designee) and Sponsor.

### **8.3 Concomitant Procedures**

Any procedure that the subject undergoes after signing the ICF throughout the duration of the study must be recorded in the eCRF along with:

- date of the procedure, and
- reason for the procedure

### **8.4 Treatment Assignment, Randomization, and Blinding**

#### **8.4.1 Treatment Assignment**

Subjects will receive open-label IMP during the Treatment Period of the study. Subjects will be randomized (Visit T1) to receive either bempedoic acid (Cohort 1) or bempedoic acid/ezetimibe FCDP (Cohort 2). The IMP will be taken Day 1 through Day 6 of the treatment period.

#### **8.4.2 Randomization**

Subjects will be randomized in a 1:1 ratio to receive either bempedoic acid (Cohort 1) or bempedoic acid/ezetimibe FCDP (Cohort 2) on Day 1 (Visit T1) of the treatment period. When the target number of subjects (8 in each cohort) is reached and all subjects have completed the 24-hour breast milk collection at the CRU, randomization will be closed. If a subject is randomized but did not complete the 24-hour breast milk collection in the CRU, she will be replaced with a new subject on the same treatment to ensure each cohort of the study has 8 evaluable subjects.

#### **8.4.3 Blinding**

This is an open-label study.

## 9. INVESTIGATIONAL MEDICINAL PRODUCT

### 9.1 Description of Investigational Medicinal Product

The IMP used for this study are described in [Table 1](#). Please see the Pharmacy Manual for detailed storage requirements and instructions.

**Table 1: Investigational Medicinal Products**

	Investigational Medicinal Product	
Product Name:	Bempedoic acid	Bempedoic acid/ezetimibe FCDP
Dosage Form:	Film-coated tablets	Film-coated tablets
Unit Dose:	180 mg	180 mg/10 mg
Container/Closure:	Bottle	Bottle
Route of Administration:	Oral, daily at similar time with or without food	Oral, daily at similar time with or without food
Physical Description:	Oval, white to off-white tablet debossed with “180” on one side and “ESP” on the other	Oval, blue tablet debossed with “818” on one side and “ESP” on the other

FCDP = Fixed combination drug product

### 9.2 Investigational Medicinal Product Supply and Control

The Sponsor will supply the IMPs for this study. The IMPs for this study, bempedoic acid and bempedoic acid/ezetimibe FCDP, have been approved by the FDA as Nexletol® and Nexlizet®, respectively. Investigational medicinal product will be distributed and released in accordance with regional and local requirements during the conduct of the study.

Investigational medicinal product will be dispensed by the Investigator or other qualified study personnel only to subjects who have provided informed consent.

### 9.3 Packaging and Labeling

Open-label IMP will be packaged in a bottle containing 30 tablets. The IMP labels will be compliant with the Code of Federal Regulations (CFR) Title 21 Section 312.6 Labeling of an Investigational New Drug.

### 9.4 Investigational Medicinal Product Adherence

On Day 2 through Day 5 subjects will document day and time IMP is taken in the Study Drug Diary and the diary will be submitted to study staff at check-in to the CRU on the evening of Day 5 (Visit T2). In addition, study staff will phone subjects on Day 2 through Day 5 to ensure subjects are taking IMP appropriately. Study staff will assess subject adherence through phone calls, review of the Study Drug Diary, and by counting the number of tablets returned at check-in to the CRU on the evening of Day 5. If a subject has missed a dose of IMP, the Sponsor will be notified immediately to determine if the subject should continue in the study or be replaced.

## **9.5      Investigational Medicinal Product Accountability**

Subjects will be instructed to return all packaging and unused IMP at check-in to the CRU on Day 5 (Visit T2) for assessment of adherence and drug accountability.

Accurate records of the receipt of all IMP shipped by the Sponsor (or designee) and the disposition of that IMP must be maintained.

All IMP records or logs must comply with applicable regulations, local law, and guidelines, and should include the:

- amount received/placed in storage area;
- amount currently in storage area;
- MED ID/Kit number for all IMP;
- dates and initials of person(s) responsible for IMP inventory (including entry/movement/disposition);
- date and amount of IMP dispensed to each subject, including unique subject identifiers;
- date that IMP was returned by subject, assessment of adherence, and relevant documentation of discrepancies;
- nonstudy disposition (e.g., lost, broken, wasted); and
- amount returned to Sponsor (or designee)/destroyed or amount destroyed per local standard operating procedure (SOP) following accountability by site monitor.

## **9.6      Investigational Medicinal Product Handling, Storage, and Disposal**

The Principal Investigator will ensure that all IMP is stored in a secure area, under recommended storage conditions. Bempedoic acid and bempedoic acid/ezetimibe FCDP must be stored at 68°F to 77°F (20°C to 25°C); excursions permitted to 59°F to 86°F (15°C to 30°C). Bempedoic acid must be stored and dispensed in the original package. Bempedoic acid/ezetimibe must be stored and dispensed in the original package protected from extreme heat and humidity. Access to IMP will be limited to those clinical site personnel authorized by the Investigator. Upon completion or termination of the study, all IMP and used and unused IMP packaging must be returned to the Sponsor (or designee) for eventual destruction unless otherwise authorized by the Sponsor. All IMP returns must be accompanied by the appropriate documentation.

## **10. STUDY PROCEDURES AND SCHEDULE OF ASSESSMENTS**

### **10.1 Informed Consent**

The subject must be adequately informed of the nature and risks of the study and understand the ICF. It is the Investigator's responsibility that no study-related procedure will be performed until the subject has been completely informed of the study, has freely consented to take part in the study, and has signed and dated an ICF approved by the Sponsor (or designee) and the Institutional Review Board (IRB). The written ICF should be prepared in the local language(s) of the potential subject population.

### **10.2 Electronic Case Report Forms (eCRFs)**

Data will be captured on eCRFs.

### **10.3 Procedures and Schedule of Assessments**

The study is comprised of 3 distinct periods: Screening Period, Treatment Period, and Washout/Follow-up Period.

The Schedule of Assessments is provided in [Appendix 1](#); however, a subject can be seen at any time for reasons of safety.

Lactation consultant visits will be scheduled anytime during the study for those subjects who desire support related to feeding/care of the infant such as preparing for the treatment and washout periods of the study, pumping breast milk for storage, introducing infant formula, introducing bottle feeding or resuming breastfeeding after Day 13 (FU1).

If the subject discontinues IMP or misses a dose, please contact the Sponsor immediately to determine if subject should continue in the study or be replaced.

#### **10.3.1 Screening Week -6 (Visit S1; Day -42 through Day -1)**

The screening period will begin with a screening visit (Visit S1) that will occur up to 6 weeks prior to randomization (Visit T1). Visit S1 will allow the Investigator to assess the subject's eligibility. After the subject provides informed consent ([Section 10.1](#)), the subject will undergo the following assessments:

- demographics;
- medical history including gestational age of infant at delivery, date of delivery, stage of lactation, length of time post-partum, smoking and alcohol intake;
- Review of current breastfeeding practices per subject report, including:
  - frequency and duration of feeds for infants fed from the breast,
  - bottles/day and ounces/day for infant's fed pumped breast milk from a bottle, and
  - use of formula supplementation (bottles/day, ounces/day and duration of supplementation);
- confirm subject is maintaining adequate breast milk production (document duration of weaning, if applicable) per subject report;

- confirm infant is able to bottle feed prior to randomization (Visit T1) per subject report;
- confirm adequate breast milk/infant formula is available to feed the infant after first dose of IMP (Visit T1) through Day 13 (Visit FU1) per subject report;
- concomitant medication review;
- adverse event review;
- physical exam;
- weight, height, and BMI;
- vital signs;
- clinical lab evaluations (blood chemistry, hematology and serology);
- assessment of renal function (eGFR calculated according to MDRD formula);
- assessment for liver disease (according to Child Pugh Classification score);
- serum pregnancy test;
- urine drug and alcohol screen; and
- schedule optional lactation consultant visit.

Note: subjects must understand that they will not be able to feed their infant breast milk produced after the first dose of IMP through Day 13.

### **10.3.2 Treatment Day 1 (Visit T1)**

Subjects who continue to meet all inclusion criteria and none of the exclusion criteria may be randomized into the study. Each subject will undergo the following assessments:

- Review of current breastfeeding practices per subject report, including:
  - frequency and duration of feeds for infants fed from the breast,
  - bottles/day and ounces/day for infant's fed pumped breast milk from a bottle, and
  - use of formula supplementation (bottles/day, ounces/day and duration of supplementation);
- confirm subject is maintaining adequate breast milk production (document duration of weaning, if applicable) per subject report;
- confirm infant is able to bottle feed prior to randomization (Visit T1) per subject report;
- confirm adequate breast milk/infant formula is available to feed the infant after first dose of IMP (Visit T1) through Day 13 (Visit FU1) per subject report;
- adverse event review;
- concomitant medicine review;
- weight;

- vital signs;
- urine pregnancy test;
- predose breast milk collection ( $\leq$ 1 hour before IMP administration);
- predose blood sample for chemistry and hematology;
- predose blood sample for plasma PK;
- administer first dose of IMP;
- dispense IMP for self-administration on Day 2 through Day 5;
- provide Study Drug Diary; and
- schedule optional lactation consultant visit.

The IMP will be administered by study staff only after the predose breast milk collection, predose chemistry and hematology, and predose plasma PK sample are collected. Subjects must be reminded to not feed their infant breast milk produced after the first dose of IMP through Day 13 of the study.

Subjects will be instructed to take IMP at the same time ( $\pm$  2 hours) every day with or without food for Day 2 though Day 5 and to complete the Study Drug Diary.

### **10.3.3 Treatment Day 2 through Day 5**

Study staff will contact the subject by phone to conduct the following:

- adverse event review;
- concomitant medication review;
- confirm subject is taking IMP appropriately;
- instruct subject to complete the Study Drug Diary;
- confirm subject is maintaining adequate breast milk production (document duration of weaning, if applicable) per subject report;
- confirm subject is discarding breast milk produced after the first dose of IMP through Day 13 per subject report;
- confirm adequate stored breast milk and/or infant formula is available to feed the infant through Day 13 of the study per subject report; and
- schedule optional lactation consultant visit.

### **10.3.4 Treatment Day 5 through Day 7 (Visit T2)**

#### **10.3.4.1 Treatment Day 5 (Evening)**

Subjects will check-in to the CRU on the evening of Day 5 for 2 overnights. With Sponsor approval, the subject may check-in to the CRU the morning of Day 6.

Subjects will return IMP to the study staff prior to the following assessments:

- adverse event review;

- concomitant medication review;
- review of Study Drug Diary and assessment of IMP adherence (if subject missed a dose or discontinued IMP, refer to [Section 9.4](#));
- confirm subject is maintaining adequate breast milk production (document duration of weaning, if applicable) per subject report;
- confirm subject is discarding breast milk produced after the first dose of IMP through Day 13 per subject report; and
- confirm adequate stored breast milk and/or infant formula is available to feed the infant through Day 13 of the study per subject report.

#### **10.3.4.2 Treatment Day 6**

The 24-hour breast milk collection will start the morning of Day 6 and end the morning of Day 7. The following assessments/procedure will be performed prior to the initiation of the 24-hour breast milk collection:

- adverse event review;
- concomitant medication review; and
- subject will pump both breasts with an electric pump until empty prior to administration of the last dose of IMP.

Once both breasts have been completely emptied on the morning of Day 6, Cohort 1 subjects will receive the Day 6 dose of bempedoic acid and Cohort 2 subjects will receive the Day 6 dose of bempedoic acid/ezetimibe FCDP. Breast milk will be collected from each subject over the next 24 hours using an electric pump at 3, 6, 9, 12, 16, 20 and 24 hours ( $\pm 30$  minutes) after Day 6 dose administration.

At each collection time point, subjects will pump both breasts until empty, breast milk collected from each breast will be mixed together and the total volume measured and recorded. Breast milk from each time point will be stored according to procedures outlined in the Laboratory Manual and [Section 11.1](#).

#### **10.3.4.3 Washout Day 7 (after completion of 24-hour breast milk collection)**

The following assessments will be performed after the 24-hour milk collection time point:

- adverse event review;
- concomitant medication review;
- physical exam;
- weight;
- vital signs;
- urine pregnancy test;
- collect blood sample approximately 24 hours after Day 6 dosing for PK and safety laboratory samples;

- confirm subject is discarding breast milk produced after the first dose of IMP through Day 13 per subject report;
- confirm adequate stored breast milk and/or infant formula is available to feed the infant through Day 13 of the study per subject report; and
- schedule optional lactation consultant visit.

Once all assessments are complete the subject will be discharged from the CRU.

#### **10.3.5 Washout Day 13 (+ 3 days)/End of Study (Visit FU1)**

On Day 13, all subjects will be contacted by phone as a post-treatment follow up visit to review:

- adverse event review;
- concomitant medication review;
- confirm subject discarded breast milk produced after the first dose of IMP through Day 13 per subject report;
- instruct subjects they may resume feeding breast milk currently being produced;
- document subject's intent to resume breastfeeding; and
- schedule optional lactation consultant visit for subjects who desire to re-establish breastfeeding.

#### **10.3.6 Serious Adverse Event Follow-up (SAE FU) and Resumption of Breast-Feeding Day 43 (+ 5 days) (Visit FU2)**

Study staff will contact subjects by phone 30 days (Day 43) after FU1 to assess for SAEs and if the patient was able to resume breastfeeding (if intended) without problems.

### **10.4 Discontinuations**

#### **10.4.1 Subjects Inadvertently Enrolled**

The inclusion and exclusion criteria for enrollment must be followed exactly and completely. If a subject who does not meet enrollment criteria is inadvertently randomized, the Sponsor should be contacted within 24 hours of identification to determine if the subject should continue in the study.

#### **10.4.2 Permanent Discontinuation of Investigational Medicinal Product**

There may be a situation where it is necessary for a subject to discontinue IMP. The Investigator should contact the Sponsor to determine if the subject should be replaced in the study. The subject will be instructed that a 7-day washout is necessary prior to resuming breastfeeding the infant. All Day 7 assessments except the 24-hour PK blood sample and breast milk collection should be performed for early termination.

#### **10.4.3 Subject Discontinuation from the Study**

If the subject discontinues prior to completing the study, the Sponsor should be contacted. If possible, an early discontinuation visit should be conducted. All Day 7 assessments except the 24-hour PK blood sample and the 24-hour breast milk collection should be performed. The subject will be permanently discontinued both from the IMP and from the study at that time. The subject will be instructed that a 7-day washout is necessary prior to resuming breastfeeding their infant breast milk produced while on IMP. If the subject discontinues prior to completing the 24-hour breast milk collection in the CRU, the subject will be replaced.

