Study Design: This is a Phase 4, open-label study that will estimate the daily infant dosage and RID of bempedoic acid and bempedoic acid/ezetimibe in the mature breast milk of healthy women who have received 6 daily doses of bempedoic acid or bempedoic acid/ezetimibe FCDP. The excretion of bempedoic acid, ezetimibe, and metabolites ESP15228, bempedoic acid glucuronide, and ezetimibe-glucuronide will be characterized in mature breast milk. Healthy lactating women who choose to stop breastfeeding their infant for the duration of the Treatment and Washout Periods will be eligible to participate once all

enrollment criteria are met. The Screening Period will be up to 42 days followed by a 6-day Treatment Period and a 7-day Washout Period. Subjects will be contacted by phone as a Post-treatment Follow-up Visit on Day 13. Once the call is complete, subjects may resume feeding their infant breast milk that is currently being produced.

**Screening Period:** The Screening Period will begin with a Screening Visit (Visit S1) that will occur up to 42 days prior to randomization (Visit T1). Visit S1 will allow the Investigator to assess the subject's eligibility and current breastfeeding practices. After the subject provides written informed consent, the subject will undergo screening assessments as outlined in [Appendix 1](#). Study staff will schedule an optional lactation consultant visit for those subjects who desire support related to feeding/care of the infant such as preparing for the treatment and washout periods of the study, pumping breast milk for storage, introducing infant formula, introducing bottle feeding or resuming breastfeeding after Day 13 (FU1). Additional lactation consultant visits may be scheduled for subjects anytime throughout the study.

**Study Population (N=16):** Healthy adult lactating females who have been breastfeeding or pumping regularly for  $\geq 4$  weeks and have agreed to discontinue breastfeeding for the 13-day duration of the treatment and washout periods

Screening (S1) Up to 6 weeks	BA or FCDP Treatment (6-day qd)						7-Day Washout						
Study Day	D1	D2	D3	D4	D5	D6	D7	D8	D9	D10	D11	D12	D13
Study Visit	T1						T2						FU1

**Day 5:** Check-in  
**Day 6:** Last dose  
 Breast milk collection 0-24 hr after Day 6 dose  
**Day 7:** Plasma PK sample 24 hr after Day 6 dose  
**D43 (FU2)** Phone call to follow-up on SAEs and ability to resume breastfeeding (if intended)

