## 6. INVESTIGATIONAL PLAN

### 6.1 Overall Study Design

This is a Phase 4, open-label study that will estimate the daily infant dosage and RID for bempedoic acid and bempedoic acid/ezetimibe FCDP and characterize the excretion of bempedoic acid, ezetimibe, and metabolites ESP 15228, bempedoic acid glucuronide, and ezetimibe-glucuronide in the mature breast milk of healthy women. The study will enroll 16 healthy lactating subjects, who will be randomized in a 1:1 ratio to receive either bempedoic acid (Cohort 1) or bempedoic acid/ezetimibe FCDP (Cohort 2), who choose to stop breastfeeding their infant for the duration of the Treatment and Washout periods (13 days). After signing the informed consent form (ICF), subjects will enter the Screening Period for up to 42 days, followed by a 6-day Treatment Period and a 7-day Washout Period. At Visit T1, subjects will be administered IMP at the clinical research unit CRU. The IMP will then be self-administered at home on Day 2 through Day 5. Study staff will phone subjects Day 2 through Day 5 to ensure IMP is being taken appropriately and remind subjects to discard breast milk produced after the first dose of IMP. Subjects will check-in to the CRU on the evening of Day 5 (with Sponsor approval the subject may check-in to the CRU on the morning of Day 6) for Visit T2 and start a 24-hour breast milk collection after the last dose of IMP on the morning of Day 6. Serum PK samples will be obtained on Day 7, approximately 24 hours after IMP administration on Day 6. Subjects will be discharged from the CRU on the morning of Day 7 approximately 24 hours after Day 6 dosing and the completion of all Day 7 assessments. At the end of the Washout Period on Day 13, all subjects will be contacted by phone for a Post-treatment Follow-up Visit (Visit FU1). Once the call is complete, subjects may resume feeding their infants breast milk that is currently being produced. On Day 43 (Visit FU2), study staff will contact subjects by phone to assess for SAEs and if the patient was able to resume breastfeeding (if intended).

Please refer to [Appendix 1](#) for a detailed Schedule of Assessments.

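### Protocol 10.4.3 words its washout instruction so that milk made on study drug appears feedable after 7 days; a probable drafting slip in an infant-safety instruction, minor to correct

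*Protocol*

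**What the plan says.** Protocol 10.4.3 covers a subject who discontinues before completing the study. She is to be instructed that "a 7-day washout is necessary prior to resuming breastfeeding their infant breast milk produced while on IMP". The same section makes the closing visit conditional: "If possible, an early discontinuation visit should be conducted". It also says that she leaves both the study drug and the study at that time.

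Protocol 10.4.2, on stopping study drug, gives the matching instruction without the closing phrase: "a 7-day washout is necessary prior to resuming breastfeeding the infant".

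Elsewhere the rule is uniform. At screening (10.3.1), "subjects must understand that they will not be able to feed their infant breast milk produced after the first dose of IMP through Day 13". On Day 1 (10.3.2), "Subjects must be reminded to not feed their infant breast milk produced after the first dose of IMP through Day 13 of the study". At the end of washout, 10.3.5 has staff "instruct subjects they may resume feeding breast milk currently being produced", and 6.1 agrees: "Once the call is complete, subjects may resume feeding their infants breast milk that is currently being produced". Protocol 13.2.7 treats infant exposure through milk as an adverse event for the infant. It requires a report if milk produced from the first dose through Day 13 is fed.

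**The concern.** The washout lowers the amount of drug in the mother, and so in the milk she goes on to make. It does nothing to milk she has already expressed. A sentence that ties a seven-day wait to milk made on treatment therefore does not fit its own purpose, and it points the reader to the milk that the rest of the protocol says must not be used.

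The instruction is operative: it sets what staff tell a subject as she leaves. Stored milk is also part of ordinary life in this trial, since subjects must have stored milk or formula available through Day 13 (Synopsis, 10.3.1). Section 4 accepts that bempedoic acid could in theory harm a breastfed infant. What is at stake is the clarity of one safety message to one small group, the women who withdraw after dosing.

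**Working it through.** No trial figure is in dispute, so the main check is a comparison of texts.

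**1. The two withdrawal instructions.** Sections 10.4.2 and 10.4.3 both require a 7-day washout before breastfeeding resumes. They differ in how the sentence ends: 10.4.2 stops at the infant, while 10.4.3 adds six words naming milk made on study drug. No other section uses that phrase.

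**2. Places that state the discard or no-feed rule for milk from the first dose.** Synopsis (Treatment Period), 6.1, 10.3.1, 10.3.2, 10.3.3, 10.3.4.1, 10.3.4.3, 10.3.5, and the Appendix 1 footnotes (footnote h in particular). That is 9.

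**3. Places that limit resumed feeding to milk then being produced.** Synopsis (Study Design), 6.1 and 10.3.5. That is 3.

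**4. Distinct places.** Sections 6.1 and 10.3.5 are on both lists, so 9 + 3 − 2 = 10. The reporting rule in 13.2.7 comes on top. The count shows that 10.4.3 is the outlier; it does not measure harm.

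**5. What seven days achieves.** Section 4.3 gives a half-life of about 24 hours for both drugs and about 98% of steady state after six daily doses.
- Reproducing the plan's figure: 1 − 0.5^(144/24) = 1 − 0.5^6 = 98.4%, which agrees.
- Residual seven days after the last dose: 0.5^(168/24) = 0.5^7 = 0.8%. For an assumed half-life of 18 to 30 hours, the range is 0.2% to 2.1%.

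This assumes that drug in milk falls in parallel with drug in plasma, which the documents do not establish. On that assumption a 7-day wait makes sense for newly produced milk, which is the meaning of 10.4.2. It does not apply to milk expressed earlier.

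**6. Which reminders reach a woman who withdraws.** Any dosed subject has had the screening and Day 1 messages. She has the Day 2 to 5 calls (10.3.3) and the check-in confirmation (10.3.4.1) only as far as she gets. The Day 7 assessments, which include a discard check (10.3.4.3), apply at early termination (10.4.3; Appendix 1, footnote b), but the visit depends on her attending. Section 10.4.3 does not say whether she still receives the Day 13 call, although 10.3.5 speaks of all subjects.

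**The case against.** The strongest reply is that a washout being necessary before something does not authorise that thing. The sentence is ungrammatical, so it has no clean literal meaning, and its workable content is the same as that of 10.4.2. Every dosed subject has already been told not to feed this milk through Day 13, and 13.2.7 requires a report if it is fed. A site following the whole protocol would not let one loose phrase override all of that.

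Most of this stands. The sentence is a condition and not a permission, and the repeated reminders keep the practical risk low. Section 10.4.2 is not faulty. What remains is that the natural reading of 10.4.3 runs against the rule it is meant to serve. It does so at withdrawal, when later contacts are least certain.

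A reader might infer that the protocol authorises feeding milk made on drug. The documents do not support that, for the reasons above. A reader might also turn the 0.8% residual into an exposure ratio, 1/0.0078 = 128, and claim that an infant could receive milk with over a hundred times the residual level. That would need drug stability in stored milk, milk levels that track plasma, and a subject who kept milk she was told to discard. The documents give none of these, and Section 4 says that nothing is known about excretion of bempedoic acid in milk. No exposure claim is made here.

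**Conclusion.** The point holds as a minor wording inconsistency in an operative infant-safety instruction. It amounts to six words in one sentence, out of line with ten other places in the protocol and with 10.4.2. The clean parallel wording makes a drafting slip the likeliest explanation.

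Endpoints, the sample size of 16 and the analysis are unaffected. Consent and site materials were not available for review, so it cannot be said whether the faulty wording reaches any subject, and the documents do not support an inference that it does.

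**What to change.** In Protocol 10.4.3 only, replace the sentence with:

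> *The subject will be instructed that a 7-day washout after the last dose of IMP is necessary before resuming breastfeeding with milk then being produced; milk produced from the first dose of IMP to the end of the washout must not be fed to the infant and, except for study samples, must be discarded.*

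This also fixes the start of the seven days, which 10.4.3 leaves unstated. The exception for study samples is needed because 10.4.3 can apply to a woman who leaves during or after the Day 6 to 7 collection. Milk from that collection is kept for assay (11.1), and footnote h of Appendix 1 leaves Day 6 out of the discard days.

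Using the same sentence in 10.4.2 is optional. Sections 6.1, 10.3.4.3, 10.3.5 and 13.2.7 need no change. The cost is one sentence, by clarification or at the next amendment, plus a check that consent and site materials do not repeat the current wording.
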